3.6. Extension of accrual period

Due to COVID, the number of observed ER events was smaller than the expected number in three SIMPRO sites as of April 2022. The study team decided to extend accrual an extra 6 months (1 additional study period) to allow for additional event collection and patient recruitment. The extension will also allow sites who recently went live to continue program optimization and stabilization. The figure (below) depicts the revised study design with Period 8.

Statistical Analysis Plan for Protocol Activity 4: Pragmatic Stepped-Wedge Cluster Randomized Trial
SIMPRO Research Center: Integration and Implementation of PROs for Symptom Management in Oncology Practice

Sequence	Group	Site	eSym version	Period 1	Period 2	Period 3	Period 4	Period 5	Period 6	Period 7	Period 8
				Mar '19 - Aug '19	Sep '19 - Feb '20	Mar '20 - Aug '20	Sep '20 - Feb '21	Mar '21 - Aug '21	Sep '21 - Feb '22	Mar '22 - Aug '22	Sept '22 - Feb '23
Med Onc live Before Surgery	Southern	BAPT	Med	Pre-live	Go-Live – 9/10/2019						
			Surg	Pre-live							Go-Live – 4/25/2022
	Northern	MMC	Med	Pre-live	Go-Live – 3/16/2020						Go-Live – 10/19/2021
			Surg	Pre-live							
	Metropolitan	DFCI	Med	Pre-live	Go-Live – 9/22/2020 (2 clinics), 11/17/2020 (1 clinic)						
			Surg	Pre-live	Go-Live – 5/4/2021 (1 clinic), 6/15/2021 (2 clinics), 10/12/2021 (1 clinic)						
Surgery live Before Med Onc	Metropolitan	LCI	Med	Pre-live							Go-Live – 9/21/2021
			Surg	Pre-live	Go-Live – 11/24/2020						
	Northern	DHMC	Med	Pre-live							Go-Live – 11/30/2021
			Surg	Pre-live	Go-Live – 4/28/2020						
	Southern	WVU	Med	Pre-live							Go-Live – 4/18/2022
			Surg	Pre-live	Go-Live – 10/25/2019						

4. Analysis for Aim 2a: Healthcare utilization, measured by the need for emergency and acute care

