4.2. General Analytic Approach

[figure not shown]
Medical Oncology and Surgery:

- The primary analysis will include data from both medical oncology (MO) and surgery (Surg) and estimate a common effect of the intervention in MO and SO. An indicator variable (MO vs. Surg), interaction between MO/Surg and Site, and interaction between MO/Surg and background time trend will be included as covariates for adjustment in multilevel generalized linear regression models.
- As a secondary analysis, for each outcome, the heterogeneity of the intervention effect by MO/Surg will also be assessed by the test for interaction between the intervention (eSym yes/no) and MO/surg using multilevel generalized linear regression models. In this analysis, the interaction between the intervention and MO/Surg will be added to the model for the primary analysis.
- As another secondary analysis, we will analyze the data from MO and Surg separately and estimate the intervention effect for each outcome. Note that this analysis is similar to the aforementioned secondary analysis including the interaction between the intervention and MO/Surg. While the aforementioned secondary analysis assumes common effects of patients' characteristics (such as age, race, gender and so on) across MO and Surg, this analysis consider these are possibly different between MO and Surg.

Determination of the intervention and length of follow-up for each episode:

- The presence /absence of the intervention (eSym+ vs. eSym-) is determined in a cross-sectional way at the time of the occurrence of the trigger event
- The follow-up period for each episode is one year from the chemotherapy start date (**MO**) and the date of discharge (**Surg**)

- The intervention determined at the trigger event will never change during the one-year of follow-up period unless another trigger event occurs (see Figure below)

- Some subjects may experience more than one trigger event (i.e., a new chemotherapy treatment plan for **MO** and a qualifying procedure for **Surg**) during the study. Thus, potentially, multiple data points/episodes will be collected from one patient.
- The primary analysis will include all these episodes other than the following episodes:
 - MO episode where its trigger event occurred after the patient was exposed to eSyM Surg, but before eSyM MO was rolled out in the patient's site.

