4.4. Multilevel Generalized Linear Regression Analysis

The primary analysis for the outcomes in Aim 2 (Table 5) will be performed via multilevel generalized linear regression models (or generalized linear mixed-effects model; GLMM).⁹ The null hypothesis for the statistical test is no intervention effect on the outcome, which indicates that the regression coefficient for the intervention indicator variable is zero. The intervention effect will be summarized in both absolute and relative terms (CONSORT Checklist Item 17b).⁷

Followings are specifications of the GLMM for the primary and secondary analyses.

- Link function
 - For binary outcomes, the logit-link will be used.
 - For count outcomes, the log-link will be used, and the follow-up time will be included as the offset in the model. (Poisson regression)
 - For time-to-event outcomes, we will use Poisson regression models, where the log-link will be used. The event indicator (1: event, 0: censoring) will be the response variable. Exposure time (i.e., days from the start date of the follow-up to either the date of the event occurrence or the end of follow-up, whichever comes first) will be included as the offset in the model.
- Treatment effect metrics
 - Following the recommendation of the CONSORT guideline,⁷ we will report the treatment effect in both absolute and relative metrics.
 - For binary outcomes, we will report odds ratio (OR) derived from the GLMM with the logit-link. In addition, we will calculate absolute difference (AD), using the resulting GLMM with G-computation. Bootstrap will be used to obtain a standard error for the estimated AD.
 - For count outcomes and time-to-event outcomes, we will report the incidence rate ratio (IRR) derived from the GLMM model. In addition, we will calculate absolute difference in incidence rate (i.e., incidence rate difference;IRD) in a similar way to calculate AD.
- Secular trend
 - Primary: Calendar time of the start date of the follow-up of each episode will be included as a continuous variable with natural cubic spline with 3 knots
 - Secondary: Period in which the trigger event occurs will be included as a categorical variable.
- Site (cluster)

- Since there are only 6 sites in this study, the conventional analysis of including cluster as random-effects is problematic due to this small number.¹⁰
- Primary: The primary analysis includes sites as fixed effects.

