6.2. Data Analysis

Analysis of Outcomes classified as Type 1:

- For descriptive purposes, we will estimate crude means for continuous outcomes and crude proportions for dichotomous outcomes and calculate corresponding 95% confidence intervals by site. The coefficient of variation is calculated using the site-specific point estimates.
- Next, we estimate the overall mean (or proportion). To this end, a weighted mean and corresponding 95% confidence interval will be calculated using the site-specific point estimates and their standard error estimates, using the inverse of the site-specific variance estimates for the weights.
- In addition, generalized linear models (GLMs) will be used to investigate factors associated with the outcome. In the GLMs, we will account for site variability by treating "site" as a fixed effect. For modeling continuous outcomes, we will use the identity link function. For dichotomous outcomes, the logit link function is used.

Analysis of Outcomes classified as Type 2:

- We will calculate the site-period-specific means (or proportions), adjusted for the factors potentially associated with the outcome. We will calculate the coefficient of variations across sites and also across periods, respectively.
- To this end, we will use generalized linear mixed-effects models (GLMMs). In GLMMs, we will account for site variability by treating "site" as a fixed-effect, secular trend by treating "period" as a fixed-effect, and within-subject variability by treating "subject" as random-effects. For modeling continuous outcomes, we will employ the identity link function. For

dichotomous outcomes, the logit link function will be utilized. G-computation will be used to derive the site-period-specific means (or proportions).

- We will also calculate the site-specific, period-specific, and overall means (or proportions) and corresponding 0.95 confidence interval by taking a weighted average of the site-period-specific mean values (or proportions) obtained through GLMMs. The reciprocal of the variance-covariance matrices of the site-period-specific mean values (or proportions) will be used as the weight.

Analysis of Outcomes classified as Type 3:

- For descriptive purposes, we will estimate crude means for continuous outcomes and proportions for dichotomous outcomes and calculate corresponding 95% confidence intervals by intervention group (eSyM+ vs. eSyM-) and site.

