- Using these results, the difference between the intervention condition (eSyM+) and the control condition (eSyM-) along with a corresponding 95% confidence interval will be calculated for each site. In addition, using the point estimates from the six sites, we will calculate the coefficient of variation of the difference between conditions.
- We will then estimate the overall between-conditions difference integrating the site-specific differences. Specifically, a weighted average and corresponding 95% confidence interval will be calculated, using the site-specific point estimates their standard error estimates, where the reciprocal of the site-specific variance estimates will be used for the weights.
- In addition, generalized linear models (GLMs) will be used to investigate factors associated with the outcome. In the GLMs, we will include the intervention indicator, “site” and other factors (i.e., age (at cancer diagnosis for medical oncology patients and at index surgery for surgical patients), sex, employment status, education, ability to pay bills, and technology confidence) as independent variables. For modeling continuous outcomes, we will employ the identity link function. For dichotomous outcomes, the logit link function will be utilized. Note that, when more appropriate (where some subjects have data from both pre- and post-intervention periods), we will use GLMMs by treating “subject” as random-effects instead of GLMs for some outcomes.

Analysis of Outcomes classified as Type 4:

- We will estimate the intervention effect on each outcome.
- To this end, analyses similar to those for Aim 2a (see Section 4) will be conducted. GLMMs will be used with the identity link function for continuous outcomes and with the logit link function for dichotomous outcomes. The intervention effect will be summarized as the mean difference and odds ratio for continuous outcomes and dichotomous outcomes, respectively, and reported with a corresponding 95% confidence interval and p-value.

Interpretation of the PROMIS scores: Note that Yost and Cella have reported minimally important difference (MID) ranges for five PROMIS domains including fatigue, pain, depression, anxiety, and physical functioning^{17,18} Cella recommends using 0.5 SD as the MID for PROMIS scales^{19,20}

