7.2. Data Analysis

Aim 2d survey methods and sampling mirrors Aim 2c (PROMIS items). Following Section 6.2 (Analysis of Outcomes classified as Type 3), we will perform the analysis for these continuous outcomes. We will use the AHRQ's CAHPS Analysis Program.^{21,22}

8. Analysis for Aim 3a: Patient adoption, clinician utilization, and their perspectives on appropriateness and acceptability

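### The PROMIS and CAHPS (Type 3) comparisons pool crude before/after differences with no calendar-time term, so any secular change is counted as an eSyM effect

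*SAP*

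**What the plan says.** **Timing of surveys.** Protocol 5.0 (Activity 4, identification of subjects) has eSyM- patients surveyed before launch at their site, once the registry exists. eSyM+ patients are surveyed after launch, starting as early as the site can manage.

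**Type 3 analysis.** SAP 6.2 computes crude means or proportions by condition and site, takes the eSyM+ minus eSyM- difference for each site from those results, and continues: "We will then estimate the overall between-conditions difference integrating the site-specific differences". The weights are inverse variances and a 95% CI is attached. A supporting GLM contains the intervention indicator, site, age, "sex, employment status, education, ability to pay bills, and technology confidence". If some patients have data from both periods, a subject random effect may be added. None of these has a period or calendar-time term.

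**CAHPS.** SAP 7.2 sends Aim 2d the same way: "Following Section 6.2 (Analysis of Outcomes classified as Type 3), we will perform the analysis for these continuous outcomes". It also names a CAHPS analysis program but lists no adjusters for it.

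**Elsewhere in the SAP.**
- Aim 2a: calendar time of episode start "will be included as a continuous variable with natural cubic spline with 3 knots" (4.4), and the "interaction between MO/Surg and background time trend will be included as covariates for adjustment" (4.2).
- Type 2: the model handles "secular trend by treating" period as a fixed effect.
- Type 4: "To this end, analyses similar to those for Aim 2a (see Section 4) will be conducted".

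The June 2024 addendum restricts the primary analysis to first episodes. It does not change the Type 3 text.

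**The concern.** A stepped wedge separates the intervention from time by comparing sites that have launched with sites that have not yet launched, at the same calendar time. The Type 3 estimate makes only within-site comparisons of early with late surveys and so gives that up. Pooling does not help: post-launch surveys are later than pre-launch surveys at every site, so a common trend pushes all six differences in the same direction.

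At stake is the reading of self-efficacy, symptom burden and satisfaction, which SAP section 2 lists among the effectiveness objectives. A drift in scores from any cause would appear as an eSyM benefit or harm, with an interval that is too confident. The SAP gives no reason for treating Type 3 differently from the other outcomes.

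**Working it through.** **Sample size.** SAP Table 4: 6 sites x (75 + 75 + 15 + 75 + 75 + 15) = 6 x 330 = 1,980, as stated. Leaving the Non-Responder versions aside, that is 900 eSyM- and 900 eSyM+ surveys. The SAP states no detectable difference for Aims 2c or 2d.

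**Inputs from the documents.** Go-live dates from the SAP 3.6 figure (first date for the multi-clinic site), and 75 v 75 surveys per site and cohort.

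**Assumptions.** The documents give no trend and no survey dates. I take a linear drift of 0.05 or 0.10 SD per year. eSyM- surveys are spread evenly over the last 3, 6 or 12 months before go-live. eSyM+ surveys are spread over the same length of time starting 1 month after go-live. Windows are cut at March 2019 and February 2023, the ends of the study periods in SAP 3.6.

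**Formulas.**
- Gap = mean eSyM+ survey date minus mean eSyM- survey date. For 3-month windows: (1 + 1.5) + 1.5 = 4.0 months. For 6-month windows: (1 + 3) + 3 = 7.0. For 12-month windows the uncut value is 13.0, and cutting at the study ends brings the mean to 12.4.
- Bias = drift x gap / 12.
- Crude SE = sqrt(2/900) = 0.0471 SD, so the 95% half-width is 1.96 x 0.0471 = 0.092 SD.
- Coverage = P(|Z + bias/SE| < 1.96).
- Detectable difference at 80% power = 2.80 x SE; crude 2.80 x 0.0471 = 0.13 SD.
- Adjusted SE: least squares with site-by-cohort fixed effects and a cohort-specific natural cubic spline in calendar time (3 inner knots).
- Break-even drift (equal mean squared error) = sqrt(adjusted SE² - crude SE²) / gap in years.

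| Window each side | Gap (months) | Bias at 0.05 / 0.10 SD per year | Crude CI coverage | Adjusted SE | Detectable, adjusted | Break-even drift (SD/year) |
|---|---|---|---|---|---|---|
| 3 months | 4.0 | 0.017 / 0.033 SD | 94% / 89% | 0.119 | 0.33 SD | 0.33 |
| 6 months | 7.0 | 0.029 / 0.058 SD | 90% / 76% | 0.106 | 0.30 SD | 0.16 |
| 12 months | 12.4 | 0.052 / 0.103 SD | 81% / 41% | 0.100 | 0.28 SD | 0.085 |

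Example, 6 months at 0.10 SD per year: bias = 0.10 x 7.0/12 = 0.058; bias/SE = 0.058/0.0471 = 1.24; coverage = 76%.

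**Does adjustment work?** Yes, because go-lives are staggered from September 2019 to April 2022. In 2,000 simulated trials at 0.10 SD per year, the adjusted interval covered 95% for the 6- and 12-month windows, against 77% and 40% for the crude interval.

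**Cohort.** The missing medical oncology/surgery term is not the cause: at 75:75 in both conditions it adds no confounding. Site-by-cohort terms are still needed once time is modelled, because the two cohorts launched 7.4 to 31.5 months apart within a site.

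**The case against.** **No drift is shown.** This stands. A reader might infer from SAP 3.6 that COVID moved these outcomes: "Due to COVID, the number of observed ER events was smaller than the expected number in three SIMPRO sites as of April 2022". That sentence reports a shortfall in event numbers against expectation at three sites. It is not a measured trend in a rate, and it says nothing about PROMIS or CAHPS. The omission is certain; the harm is conditional.

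**The cure can be less accurate than the disease.** This also stands. With 6-month windows the crude root mean squared error is sqrt(0.029² + 0.0471²) = 0.055 SD at 0.05 SD per year and 0.075 SD at 0.10, against 0.106 SD adjusted. With 12-month windows it is 0.070 and 0.113 SD, against 0.100. With no drift, adjustment more than doubles the SE for nothing. So the crude estimate should not be discarded. What adjustment buys is an interval that does not depend on zero drift.

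**Long survey windows exaggerate the problem.** If surveys filled the whole pre- and post-launch phases, the gap would be 24.5 months and coverage 42% / 1%. The Protocol does not support that picture: control surveys wait for the registry, eSyM+ surveys begin promptly, and administration stops once the targets are met. I place no weight on those figures.

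**The comparison is only descriptive.** Partly fair. The first Type 3 step is labelled descriptive, and no Type 3 test or power claim is planned. But the pooled difference is introduced as an estimate with a 95% CI. The GLM's stated purpose is to explore associated factors, so the pooled figure is the only between-condition effect estimate named for these outcomes.

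**Conclusion.** The concern holds for PROMIS and CAHPS. The planned estimate and interval attribute any common secular change to eSyM, although the SAP models time for Aim 2a, Type 2 and Type 4 outcomes. Under the assumed drifts and windows of 3 to 12 months, the bias runs from about 0.02 to 0.10 SD and coverage from 94% down to 41%. All these shifts are well below the 0.5 SD that the SAP cites as the minimally important difference for PROMIS (it cites none for CAHPS). The practical risk is therefore a small spurious effect reported with too narrow an interval. A spurious difference of clinically important size is not indicated.

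The documents do not support the stronger conclusions that these results will be biased, that the bias favours eSyM, or that the trial's main result is confounded. Drift size and direction are unknown, and the Aim 2a primary analysis already adjusts for calendar time.

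**What to change.** In SAP 6.2 (Type 3), and by reference in 7.2:

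1. Add a model-based between-condition estimate with intervention, site, cohort, site-by-cohort and cohort-specific continuous calendar time, following 4.2 and 4.4.
2. Report it together with the crude pooled difference, and label the latter an unadjusted before/after contrast.
3. State that any claim of an eSyM effect on PROMIS or CAHPS rests on the time-adjusted interval.

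No new data are needed. The calendar date can be that of the trigger event: Protocol 12.0 (Activity 4c) already collects surgery and chemotherapy dates for all denominator patients, and 4.4 uses the start of follow-up in the same way.

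**Cost.** SAP wording, and precision: the SE rises from 0.047 to 0.10-0.12 SD and the difference detectable with 80% power from 0.13 to about 0.28-0.33 SD. That is still below 0.5 SD. The shortest windows carry the least bias and the largest precision loss. At low drift the crude estimate has the smaller mean squared error, which is why both should be shown.

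**Limit.** The Protocol identifies eSyM- patients up to 6 months after treatment but eSyM+ patients at 30-60 days. A calendar-time term does not remove any difference due to time since treatment, so that needs its own clarification.

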Under a HIPAA waiver, study staff will run reports in Epic as part of the eSyM registry and/or to identify patients meeting eSyM registry criteria to identify medical and surgical patients for eSyM+, eSyM-, eSyM+ Non-Responder SASS questionnaires, and patient qualitative interviews. Select eSyM- patients will be identified and surveyed before eSyM's launch at their site but after the registry has been created, ensuring that they have never been exposed to the program but would have been eligible to use it. Patients eligible to complete the eSyM- questionnaire will be identified using the patient registry and/or a site-developed Epic report to identify patients who had a qualifying surgery or new chemo start within the last 6 months. Patients eligible to complete the eSyM+ and eSyM+ Non-Responder questionnaires will be identified using the registry after eSyM has been launched at their site and 30-60 days after their surgery or new chemotherapy. The eSyM+ SASS questionnaire will be distributed to patients who were assigned to eSyM and completed at least one eSyM questionnaire. The eSyM+ Non- Responder SASS questionnaire will be distributed to patients who were assigned to the eSyM program but never completed an eSyM questionnaire. Sites may begin distributing eSyM+ and eSyM+ Non- Responder questionnaires as soon as they are able to do so after go-live and will continue until a minimum of 75 eSyM+ surveys and a minimum of 15 eSyM+ Non-Responder surveys have been collected for the medical oncology and surgery versions. Patients eligible to participate in the qualitative interviews will be identified using Epic reports and invitations will be sent to patients meeting eSyM program eligibility. Patients may or may not have previously completed SASS or eSyM questionnaires. Interviews will be conducted until thematic saturation is reached, or until 100 interviews have been completed, whichever is reached first.

In addition, under a HIPAA waiver, email and postal addresses will be obtained for all eSyM+, eSyM-, eSyM+ Non-Responder and qualitative interview patients. Email and postal addresses will be utilized to share the SASS questionnaire invitation through REDCap and/or mailing (see Appendix Z) and to send the interview invitations and consent forms via email and/or mailing (see Appendix SS and QQ).

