The questionnaire will stop being administered once a minimum of 1,980 total surveys have been received in accordance with the above breakdown. (**Table 4**) *** Total number of SASS participants through surveys can be larger or smaller depending on availability.*

A small subset of eSyM- and eSyM+ patients will be invited to take part in a one-time qualitative interview. Patients may or may not have previously completed SASS or eSyM questionnaires. Interviews will continue until thematic saturation is reached, or until 100 interviews are completed, whichever is reached first.

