6.1. Outcomes and summary measures

The outcomes investigated in Aim 2c of the SIMPRO study are classified into four groups, depending on the data source and data collection schedule. **Table 12** shows the details of the groups and the disposition of each outcome in Aim 2c.

Table 12: Outcomes in Aim 2c		
Type	Outcome Type in the SIMPRO study	Example outcomes in Aim 2c
1	Measured at one single time point only either in post-intervention (the intervention condition) or in pre-intervention (the control condition) for all or selected subjects (patients or providers)	eSyM decline (1 st time)
2	Measured at multiple time points (periodically) only in post-intervention period for all or selected subjects (patients or providers)	eSyM logins per patient per month
		Frequency of patient eSyM reports with severe symptoms
3	Measured from selected subjects (patients or providers) at a single time point, which could be during the pre-intervention period or the post-intervention period. For some subjects, data may be collected at both periods.	PROMIS items (self-efficacy for managing symptoms, pain interference, fatigue, and physical function)
4	Measured periodically through the SW-CRT design from all eligible subjects.	MyChart activation (binary outcome)
		MyChart logins per patient per month

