Approach to missing data for PROMIS scores: Because a random missing mechanism assumption is not verifiable, we will use several methods to handle missing observations. Specifically, we will perform: (1) mean value; (2) worst-case; (3) best-case; and, (4) multiple imputations.¹³

7. Analysis for Aim 2d: Patients' satisfaction with their cancer care

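### Mean-value filling of missing PROMIS scores is an unranked option with no variance correction; used for inference, it distorts the interval or the effect and gives sites more weight as more of their scores go missing

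*SAP*

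**What the plan says.** SAP Table 12 (section 6.1) places the "PROMIS items (self-efficacy for managing symptoms, pain interference, fatigue, and physical function") among the Type 3 outcomes. For these, section 6.2 takes the eSyM+ minus eSyM- difference at each site and then combines the six sites: "a weighted average and corresponding 95% confidence interval will be calculated", "where the reciprocal of the site-specific variance estimates will be used for the weights". A regression model with site as a covariate is also planned.

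The paragraph on missing PROMIS scores gives its reason for running more than one method: "Because a random missing mechanism assumption is not verifiable, we will use several methods to handle missing observations". The methods are "1) mean value; (2) worst-case; (3) best-case; and, (4) multiple imputations". The SAP does not say which method carries the result, which mean is used (site by condition, site, or overall), or how the variance is adjusted after filling.

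Survey targets are equal across sites. The Protocol (section 5.0, Activity 4) asks each site, for each of medical oncology and surgery, for "a minimum of 75 eSyM+ surveys and a minimum of 15 eSyM+ Non-Responder surveys", and SAP Table 4 adds 75 eSyM- surveys. Collection stops "once a minimum of 1,980 total surveys have been received", but SAP section 3.3 adds: "Total number of SASS participants through surveys can be larger or smaller depending on availability".

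**The concern.** Filling a gap with a mean adds a value with no spread and then counts it as a patient. The observed variance falls while the apparent sample size stays at its full value, so the standard error is too small. Section 6.2 then uses that same variance to set the site weights. Inverse-variance weighting is meant to favour the sites with the most information. After mean filling, a site looks more precise because its scores are missing.

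At stake are the intervals for the PROMIS comparisons in Aim 2c and the balance of sites behind the pooled difference. With four methods of equal standing, a reader also cannot tell in advance which answer counts.

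**Working it through.** **Inputs.** The SAP gives no PROMIS sample-size calculation, SD or missing rate, so there is no plan figure to reproduce. Table 4 is internally consistent: 6 sites x 2 cohorts x (75 + 75 + 15) = 1,980. The missing shares below are assumptions. Missingness is taken as completely at random and equal in the two conditions.

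**Step 1: filling with the site-by-condition mean.** Take n scores per site and condition, SD s, share m missing.
- Apparent SE of a mean: about s x sqrt((1-m)/n)
- Correct SE: s / sqrt(n(1-m))
- Ratio: 1-m (at n = 75 the finite-sample ratio is 0.899, 0.799 and 0.698 at 10, 20 and 30% missing)
- Coverage of a nominal 95% interval: 2 x Phi(1.96(1-m)) - 1

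| Missing share m | Interval width relative to correct | Coverage |
|---|---|---|
| 5% | 0.95 | 93.7% |
| 10% | 0.90 | 92.2% |
| 20% | 0.80 | 88.3% |
| 30% | 0.70 | 83.0% |

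A simulation of the pooled estimate (six sites, 75 per condition, difference 0.3 SD, 3,000 runs) gave 90.7, 87.2 and 81.6% at 10, 20 and 30%. Intervals from the observed scores alone covered 93.9 to 95.6% across all the simulated settings.

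**Step 2: site weights.** The weight after filling is proportional to n/((1-m)s^2). On observed data it is proportional to n(1-m)/s^2. Filling therefore multiplies a site's weight by 1/(1-m)^2: 1.23 at 10%, 1.56 at 20% and 2.04 at 30%. For six sites with equal n and SD:

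| Missing share | 0% | 5% | 10% | 15% | 20% | 30% |
|---|---|---|---|---|---|---|
| Weight, observed data | 19.2% | 18.3% | 17.3% | 16.3% | 15.4% | 13.5% |
| Weight, mean-filled | 14.2% | 15.0% | 15.8% | 16.8% | 17.8% | 20.3% |

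The 30% site gets 1/0.70 = 1.43 times the weight of the complete site, when it should get 0.70 times. In units of s, with n = 75, the pooled SE is reported as 0.0616 when the true SE of that weighted estimate is 0.0737. The ratio is 0.84 and coverage is 89.9% (simulated 89.4%).

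**Step 3: does the site with the most missing data always get the most weight?** No.
- With survey numbers of 120, 75, 75, 75, 75 and 75 per condition and missing shares of 5, 5, 10, 10, 20 and 30%, the 120-survey site gets 22.1% and the 30%-missing site 18.7%.
- With equal n and the missing shares in the table above, raising the SD of the 30%-missing site by 25% drops its weight to 14.1%, the lowest of the six.

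**Step 4: filling with a mean across conditions.** The difference and its SE now shrink together by about (1-m). At zero effect and 30% missing, simulated coverage stays at 94.8%. At a true difference of 0.30 SD and 30% missing, the estimate falls to 0.21 SD and coverage to about 60%. Weights again rise with missingness, from about 14% for the complete site to about 21% for the 30%-missing site.

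**The case against.** The strongest reply is that section 6.2 describes a set of parallel analyses, chosen because the missing mechanism cannot be checked, and that multiple imputation is one of them. No text makes the mean-filled version the reported result. A reader might infer that the PROMIS intervals will be too short; the documents do not support that. The fault reaches the conclusion only if the mean-filled analysis is used for inference.

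Three other strong readings also fail. That the site with the most missing scores gets the most weight is true at equal survey numbers and SDs, but SAP section 3.3 lets numbers vary, and the counterexamples above reverse the ranking. That the pooled difference is pulled towards poorly completing sites needs site effects that differ; under a common effect the wrong weights cost precision but do not shift the estimate. Large missing shares have no basis in the documents: survey targets count questionnaires received, so on that reading m is the share of unscored PROMIS measures within returned surveys, and it may be small. At 5% the coverage loss is about one point. The planned regression with site as a covariate does not use the reciprocal-variance weights either.

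Two things remain. Nothing labels mean filling as descriptive or as a sensitivity analysis. Nor does it serve the stated purpose: filling with the site-by-condition mean returns each site's observed-score estimate unchanged, so it tests no departure from random missingness and changes only the variance and the weights. Leaving the type of mean unstated does not rescue it, because a mean across conditions shrinks a real effect.

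**Conclusion.** The point holds as a fault in one of four stated analyses, made consequential because no main method is named. With site-by-condition filling, the SE is about (1-m) of its correct value and coverage is about 94, 92, 88 and 83% at 5, 10, 20 and 30% missing. A site's pooling weight moves the wrong way, by 1/(1-m)^2 relative to observed data. With filling across conditions, a real effect shrinks by about (1-m).

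These sizes rest on missingness completely at random at the same rate in both conditions, and on assumed rates. The effect on the trial is limited to the Aim 2c PROMIS comparisons, and there only if the mean-filled result is used for inference. The primary outcome, emergency department treat-and-release by Day 30, is unaffected. The change is worth making because it is cheap and the sound method is already listed.

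**What to change.** In SAP section 6.2:
- Name multiple imputation as the main handling of missing PROMIS scores, with variances combined by Rubin's method within each site before the sites are pooled, so that the weights reflect the missing scores. SAP section 4.6 already sets out imputation models and Rubin's pooling for missing rurality and can serve as the template.
- Drop mean-value filling, or keep it as descriptive only, with no confidence interval or pooling weights taken from it.
- Label worst-case and best-case as sensitivity bounds.

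The cost is a few sentences of SAP text and no new data. Intervals will be somewhat wider than the mean-filled ones.
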